3.0 ELIGIBILITY CRITERIA

Patient MRN (COH Only)	Patient Initials (F, M, L):
Institution:	

Participants must meet all of the following criteria on screening examination to be eligible to participate in the study:

3.1 Inclusion Criteria

- __1. Documented informed consent of the participant and/or legally authorized representative.
 - Assent, when appropriate, will be obtained per institutional guidelines
- __2. Be willing to provide archival tissue of a biopsy that was performed after the frontline systemic therapy.
 - If unavailable, exceptions may be granted with Study PI approval.

Δαρ	Criteria.	Perfor	rmance	status
Auc	CHILEHIU,	reiioi	munce	stutus

- __3. Age: ≥ 18 years
- 4. ECOG ≤ 2

Nature of Illness and Illness Related Criteria

- __5. Histologically confirmed diagnosis of diffuse large B-cell lymphoma according to the WHO classification, with hematopathology review at the participating institution. Subtypes of DLBCL including transformed indolent lymphomas (TIL), primary mediastinal large B-cell lymphoma (PMBCL), and high-grade B-cell lymphoma not otherwise specified (HGBCL-NOS) are eligible.
- __6. Biopsy-proven relapsed or refractory disease after 1 line of frontline CD20-directed immunotherapy with anthracycline- or anthracenedione-based multi-agent chemotherapy. Monotherapy with rituximab or other CD20-directed immunotherapy prior to frontline chemotherapy or as maintenance therapy, and radiation therapy in a limited field or as a part of the frontline treatment plan are permitted.
- ___7. Prior lymphoma therapy should be completed at least 2 weeks before start of protocol therapy.
- 8. Measurable disease by CT or PET/CT scan with one or more sites of disease ≥ 1.5 cm in longest dimension.
- __9. Considered eligible for high-dose chemotherapy followed by ASCT.
- __10. Fully recovered from the acute toxic effects (except alopecia) to ≤ Grade 1 to prior anti-cancer therapy.

Clinical Laboratory and Organ Function Criteria

11. Without bone marrow involvement: ANC ≥ 1,000/mm ³	ANC:	Date:
With bone marrow involvement: ANC ≥ 750/mm³		
NOTE: Growth factor is not permitted within 7 days of ANC assessment unless cytopenia is secondary to disease involvement.		
12. Without bone marrow involvement: Platelets ≥ 100,000/mm ³	Plts:	Date:
With bone marrow involvement: Platelets ≥ 75,000/mm ³		
NOTE: Platelet transfusions are not permitted within 7 days of platelet assessment unless cytopenia is secondary to disease involvement.		

Patient MRN (COH Only)	Patient Initials (F, M, L):
Institution:	

13. Hemoglobin ≥ 8 g/dL (no erythropoietin and/or pRBC transfusion allowed within 7 days prior to screening) Exception: unless cytopenia is secondary to disease involvement.	Hgb:		Date:	
14. Total bilirubin ≤ 1.5 X ULN If hepatic involvement by lymphoma, or Gilbert's disease: ≤ 3X ULN		Bil: Liver involvement: Y/N Gilbert's disease:		
15. AST \leq 2.5 x ULN If hepatic involvement by lymphoma: AST \leq 5 x ULN	ULN: AST: Liver involver	ment: Y/N	Date:	
16. ALT \leq 2.5 x ULN If hepatic involvement by lymphoma: ALT \leq 5 x ULN	ULN: ALT: Liver involver	ment: Y/N	Date:	
17. Creatinine clearance of ≥ 50 mL/min per 24 hour urine test or the Cockcroft-Gault formula or CrCl	Serum (Date:	
18. If not receiving anticoagulants: International Normalized Ratio (INR) OR Prothrombin (PT) ≤ 1.5 x ULN If on anticoagulant therapy: PT must be within therapeutic range of intended use of anticoagulants		icoagulant r: Yes/No	Date:	
19. If not receiving anticoagulants: Activated Partial Thromboplastin Time (aPTT) ≤ 1.5 x ULN If on anticoagulant therapy: aPTT must be within therapeutic range of intended use of anticoagulants		icoagulant r: Yes/No	Date:	
20. Women of childbearing potential (WOCBP): negative urine or serum pregnancy test If the urine test is positive or cannot be confirmed as negative, a serum pregnancy test will be required	Urine:	Serum:	Date:	

Patient MRN (COH Only)	Patient Initials (F, M, L):
Institution:	

Contraception

Agreement by females **and** males of childbearing potential* to use an effective method of birth control or abstain from heterosexual activity for the course of the study through at least 12 months after the last dose of polatuzumab vedotin or rituximab for women, at least 5 months following the last dose of polatuzumab vedotin or 3 months following the last dose of rituximab for men, and at least 6 months following the last dose of ifosfamide, carboplatin, or etoposide for both women and men.

* Childbearing potential defined as not being surgically sterilized (men and women) or have not been free from menses for > 1 year (women only).

3.2 Exclusion Criteria

Prior and	l concomi	itant ti	herapies	

1. Patients who are not hematopoietic stem cell transplant candidates are excluded.	
2. Prior solid organ transplantation.	
3. Systemic steroid therapy or any other form of immunosuppressive therapy for lymphoma symptom cont must be tapered down to ≤ 10 mg/day prednisone or equivalent. Exceptions are: - Inhaled or topical steroids	rol

- Adrenal replacement doses > 10 mg daily prednisone equivalents in the absence of active autoimmune

Other illnesses or conditions

disease.

4. Peripheral neuropathy ≥ grade 2 or demyelinating form of Charcot-Marie-Tooth disease.
5. Known active central nervous system (CNS) involvement by lymphoma, including leptomeningea involvement.
6. Active infection requiring systemic therapy.
7. Other active malignancy requiring therapy. Exceptions include basal cell carcinoma of the skin or squamous cell carcinoma of the skin that has undergone potentially curative therapy or in situ cervical cancer.
8. History of severe allergic reactions attributed to compounds of similar chemical or biologic composition to study agents.
9. Recent major surgery (within 4 weeks) prior to start of protocol therapy, other than for diagnosis.
10. Symptomatic cardiac disease (including symptomatic ventricular dysfunction, symptomatic coronary artery disease, and symptomatic arrhythmias), cerebrovascular event/stroke or myocardial infarction within the past 6 months. See Appendix C.

(defined as negative HBsAg and positive hepatitis B core antibody [HBcAb]) are eligible if HBV DNA is undetectable. Patients who are positive for HCV antibody are eligible if PCR is negative for HCV RNA. Testing to be done only in patients suspected of having infections or exposures.

_11. Known active hepatitis B virus (HBV) or hepatitis C virus (HCV) infection. Patients with past HBV infection

	12.	Known	active	human	immuno	deficiency	virus	(HIV)	infection.	Subjects	who	have	an	undetec	table	or
un	quar	tifiable	HIV vir	al load w	vith CD4	> 200 and a	are on	HAAR	T medicati	on are all	owed.	Testi	ng to	be don	e only	ı in
pa	tient	s suspe	cted of	having i	nfections	or exposu	ires.									

13. Hi	story of or current progres	sive multifocal leukoencephalopathy (PML).
--------	-----------------------------	--

__14. Females only: Pregnant or breastfeeding.

Patient MRN (COH Only)	Patient Initials (F, M, L):
Institution:	

__15. Any other condition that would, in the Investigator's judgment, contraindicate the patient's participation in the clinical study due to safety concerns with clinical study procedures.

Noncompliance

__16. Prospective participants who, in the opinion of the investigator, may not be able to comply with all study procedures (including compliance issues related to feasibility/logistics).

Eligibility Confirmed* by (Choose as applicable):	Print Name	Signature	Date		
☐ Site PI					
Authorized study MD					
Study Nurse					
Study CRA/ CRC					
Other:					
*Eligibility should be confirmed per institutional policies.					

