5.6 Salvage (PolaR-ICE)

- See Section 5.14 regarding G-CSF administration as supportive care.
- 2-3 cycles of PolaR-ICE:
 - All patients are planned to receive 2 cycles of PolaR-ICE.
 - Patients with PR after 2 cycles will receive an additional cycle of PolaR-ICE (3 cycles total). Patients with CR or SD after 2 cycles may receive an additional cycle of PolaR-ICE (3 cycles total) at the treating physician's discretion.
- If one agent is discontinued due to toxicity, then the participant may continue to receive the other
 protocol therapy agents. Note: if an agent is discontinued, administration of R-ICE should be prioritized
 since it is the standard of care and as the use of polatuzumab vedotin as part of salvage therapy remains
 investigational.

Timing and windows for imaging are detailed in Section 10.0.

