5.8.3 Rituximab, Ifosfamide, Carboplatin, Etoposide (R-ICE)

Administer R-ICE per institutional standards. Inpatient or outpatient administration is allowed. Dosing should be based on the patient's baseline height and weight (C1D1, pre-dose) or per institutional standards. Doses will be adjusted for patients who experience a ≥10% change in weight during the study. Rounding is permissible according to institutional standards.

Mesna will be given with ifosfamide according to institutional standards.

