6.2 Rituximab

The most common (≥25%) adverse reactions in clinical trials for NHL and CLL were infusion reactions, fever, lymphopenia, chills, infection, asthenia, and neutropenia.

According to the package insert for rituximab, rituximab can cause:

- *Infusion reactions:* Rituximab can cause severe, including fatal, infusion reactions. Severe reactions typically occurred during the first infusion with time to onset of 30-120 minutes.
- Severe mucocutaneous reactions: These reactions include paraneoplastic pemphigus, Stevens-Johnson syndrome, lichenoid dermatitis, vesiculobullous dermatitis, and toxic epidermal necrolysis. The onset of these reactions has been variable and includes reports with onset on the first day of rituximab exposure.
- Hepatitis B virus reactivation: Hepatitis B virus (HBV) reactivation, in some cases resulting in fulminant hepatitis, hepatic failure and death, can occur in patients treated with drugs classified as CD20-directed cytolytic antibodies, including rituximab.
- Progressive Multifocal Leukoencephalopathy (PML): JC virus infection resulting in PML and death can occur
 in rituximab-treated patients with hematologic malignancies.
- Tumor lysis syndrome: Acute renal failure, hyperkalemia, hypocalcemia, hyperuricemia, or hyperphosphatemia from tumor lysis, some fatal, can occur within 12-24 hours after the first infusion of rituximab in patients with NHL. A high number of circulating malignant cells (≥25,000/mm3) or high tumor burden, confers a greater risk of TLS.
- Infections: Serious, including fatal, bacterial, fungal, and new or reactivated viral infections can occur during and following the completion of rituximab-based therapy.
- Cardiac arrhythmias and angina
- Renal toxicity
- Bowel obstruction and perforation

Cytopenias

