12.3 Sample Size and Accrual Rate

The minimum study accrual will be 4 patients, when both dose levels are found to be not tolerable during the safety lead-in portion. The expected total sample size for the study is 40 evaluable patients, assuming that dose level 1 (starting dose level) is safe and passes the first stage response evaluation in Phase 2, and safety lead-in patients are also evaluable for response. However if dose level 1 is not tolerable and dose level -1 is tolerable, the study will need to accrue up to 48 evaluable patients for the safety lead-in and phase 2 evaluations. Accounting for up to 10% inevaluable patients for unacceptable toxicity evaluation during Safety lead-in or inevaluable for response during Phase 2, the maximum accrual for the study is estimated to be 53 patients. Given that this is a multicenter study including high-volume DLBCL centers, we anticipate completing study accrual within 24 months.

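### Exclusion 11 ties eligibility in past HBV to undetectable HBV DNA but restricts testing to suspected patients, so an unsuspected patient with no result on file can start rituximab with HBV status unknown

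*Combined protocol and SAP*

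**What the plan says.** Section 3.2, item 11, has three parts:

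- It excludes "Known active hepatitis B virus (HBV) or hepatitis C virus (HCV) infection".
- It defines past HBV as negative HBsAg with positive HBcAb, and says that such patients "are eligible if HBV DNA is undetectable".
- It limits testing: "Testing to be done only in patients suspected of having infections or exposures".

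The synopsis repeats the exclusion of known active infection and refers back to Section 3.2.

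On exposure, Section 5.6 states that "All patients are planned to receive 2 cycles of PolaR-ICE", and Table 5.3 puts rituximab on Day 1 of each salvage cycle. On hazard, Section 6.2 lists HBV reactivation under CD20-directed antibodies, including rituximab, "in some cases resulting in fulminant hepatitis, hepatic failure and death".

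**The concern.** Item 11 sets a safety condition and, in the same item, limits the test that would show to whom it applies. A person with past HBV who has no symptoms and no recognised exposure gives the investigator no reason for suspicion. If no earlier result exists either, the protocol does not call for serology, the patient is never classified as having past HBV, and the DNA condition is never reached. An HBsAg-positive patient in the same position is not known to have active infection, so the first part of item 11 does not catch that patient either.

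At stake is a harm that the protocol itself describes as potentially fatal, in a regimen where every patient is planned to receive rituximab. The decision to prevent or monitor reactivation also depends on knowing the patient's status.

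**Working it through.** There is no figure in the plan to reproduce. The check is a reading of the text, in three steps.

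**Step 1. Which patients does item 11 reach?** Sort patients by what is known before the first dose.

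| Patient | What the protocol leads to |
|---|---|
| Infection or exposure suspected | Tested; the active and past HBV criteria can be applied |
| Not suspected, positive HBcAb or HBsAg on file | Status known; the criteria can be applied. Section 4.1 allows clinically obtained results to be used |
| Not suspected, negative serology on file | No condition triggered, although an old negative does not prove current status |
| Not suspected, nothing on file | No serology called for; the DNA condition cannot be applied |

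Only the last row is the gap.

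**Step 2. Does any other provision close the last row?**

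- Eligibility checklist (Section 3.1, items 11 to 20): result and date fields for blood counts, liver and renal function, coagulation and pregnancy; none for HBV.
- Registration packet (Section 4.2.3): no HBV result listed. The coordinating center may ask for more documents in some cases.
- Study calendar (Section 10.0 and footnotes): blood count, chemistry, coagulation and pregnancy tests; no HBsAg, HBcAb or HBV DNA at any visit.
- Consolidation criteria (Section 5.7.1): liver limits, but no HBV test.
- Prophylaxis (Section 5.14): required antiviral cover is named for HSV and VZV. Cover for other agents is allowed where clinically indicated, which for HBV presupposes that the status is known.
- Liver chemistry: limits at entry (Section 3.1, items 14 to 16), then chemistry including bilirubin, ALT and AST on Day 1 of every salvage and consolidation cycle, at end of salvage and at the 30-day safety visit (Section 10.0, footnote p). Section 14.2.1 makes a combined transaminase and bilirubin rise, or a transaminase rise with jaundice, an event of special interest. These detect liver injury; they do not identify past HBV in a patient with normal liver tests.

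None of these requires HBV status before the first dose.

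**Step 3. Can the number affected be estimated?** It would be

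patients treated × share not suspected and with no result on file × share of those with past or active HBV.

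Section 12.3 bounds the first factor: "the maximum accrual for the study is estimated to be 53 patients". The documents give neither of the other two. If every site screens under local policy, the second factor is 0 and so is the product. Otherwise the product is an unknown fraction of at most 53. No estimate between these bounds can be supported. Counting rituximab doses would not help, because the unit at risk is a patient with unrecognised HBV, not a dose.

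**The case against.** The strongest reply is that the gap may be empty in practice. Section 5.8.3 says "Administer R-ICE per institutional standards", so a site may screen every patient before rituximab whatever item 11 says. Section 8.2 refers to the package inserts. Every patient enters "after 1 line of frontline CD20-directed immunotherapy", so many may already have serology on file. Section 3.1, item 9, requires candidates for high-dose therapy and ASCT, and a transplant work-up may include viral testing. Section 3.2, item 15, lets the investigator exclude on safety grounds. Suspicion under item 11 covers exposure as well as infection. The same restriction appears in item 12 for HIV, which suggests deliberate policy.

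Most of this stands as mitigation, and it rules out stronger readings. A reader might infer that patients with HBV will in fact receive rituximab untested, or that the DNA condition never works. The documents support neither: local standards and earlier results are not visible here, and the condition does work wherever a result exists. What does not stand is the step from mitigation to closure. Each safeguard is optional, depends on local practice, or acts only once liver injury shows. If the restriction was deliberate, the protocol gives no reason for it.

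It can also be objected that requiring serology while leaving prophylaxis to the sites still relies on local practice. That is partly true, but a site cannot apply its own HBV policy to a status that nobody has established.

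**Conclusion.** The point holds in a limited form. For an unsuspected patient without an HBV result on file, item 11 cannot be operated as written before the first rituximab dose, and no other provision requires the missing information. This rests on the text of Sections 3, 4, 5, 6.2, 10.0 and 14.2.1, and on no assumption about prevalence.

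Its size in patients is unknown and may be zero. Two further inferences should be resisted. One is that every HBsAg-positive patient should be excluded outright: the present criterion concerns known active infection, and nothing in the documents supports replacing it with a blanket rule. The other is that the trial's statistical properties suffer: the CR endpoint, type I error and power do not depend on this point.

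**What to change.** Replace the testing sentence of item 11 with wording to this effect:

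*HBsAg and HBcAb results are required for every patient before the first rituximab dose; a documented clinical result obtained at or after the lymphoma diagnosis is acceptable. If either is positive, HBV DNA is tested during screening and the existing active and past HBV criteria are applied to the result. HCV testing remains limited to patients in whom infection or exposure is suspected.*

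Add result and date fields for HBsAg, HBcAb and, where applicable, HBV DNA to the eligibility checklist, and a screening row to the Section 10.0 calendar. Exempt HBsAg and HBcAb serology from the 14-day laboratory window in footnote o, so that results on file can count. Because the checklist is part of the registration packet, the result will normally be in hand at registration. Prophylaxis or DNA monitoring in HBcAb-positive patients follows institutional standards under Section 5.14. The HIV rule in item 12 stays as it is.

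Cost: amendment wording, the checklist fields and one calendar row; at most one round of serology per screened patient without a result on file (no more than 53 among accrued patients, plus any screened but not registered); and HBV DNA only where serology is positive. Section 17.10 does not let research procedures be charged to participants or insurers, so the amendment should say whether the test is standard of care or paid for by the study. An occasional added exclusion is possible. Accepting older serology leaves a small residual risk, because a past negative does not prove current status.

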4.0 PARTICIPANT ENROLLMENT

NOTE: Sites must meet activation requirements prior to enrolling participants.

4.1 Pre-Enrollment Informed Consent and Screening Procedures

Diagnostic or laboratory studies performed exclusively to determine eligibility will be done only after obtaining written informed consent. Studies or procedures that are performed for clinical indications (not exclusively to determine study eligibility) may be used for baseline values and/or to determine pre-eligibility, even if the studies were done before informed consent was obtained.

The informed consent process is to be fully documented (see Section 17.4), and the prospective participant must receive a copy of the signed informed consent document. Screening procedures are listed in Section 10.0 (Study Calendar).

4.2 Participant Enrollment

4.2.1 COH DCC Availability and Contact Information

Eligible participants will be registered on the study centrally by the Data Coordinating Center (DCC) at City of Hope.

DCC staff are available between the hours of 8.00 am and 5.00 pm PST, Monday through Friday (except holidays).

o E-mail: [contact]

4.2.2 Slot verification and reservation

A designated study team member should email the DCC to verify current slot availability, and to reserve a slot for a specific prospective subject (provide DCC with subject initials), including a tentative treatment date. Slots can only be held for a limited time, at the discretion of the study PI.

The DCC should be notified of cancellations of prospective participants holding slots as soon as possible.

4.2.3 Registration Process

Allow up to 24 hours for the DCC to review. To register a participant the subsequent procedure is to be followed:

- 1. The study team should contact the DCC via email to provide notification regarding the pending registration and communicate desired timeline of the registration, especially if it must be completed promptly to meet the registration window.
- 2. The study team will email a **Complete Registration Packet** to the DCC, which consists of a copy of the following documents:
 - Registration Cover Sheet (Appendix D)
 - Completed eligibility checklist (printed from Section 3.0 of the protocol) with required signature(s)
 - Signed Informed Consent
 - Signed HIPAA authorization form (if separate from informed consent)
 - Signed subject's bill of Rights (California only)
- 3. In some cases, the DCC may request additional documentation prior to registration. Please refer to the Work Instruction Reviewing Packets and Registering Subjects for more information. A copy of this work instruction can be provided by the DCC, upon request.
- 4. When all documents are received, the DCC will review and work with the study team to resolve any missing elements. Any missing documents may delay registration. A participant failing to meet all requirements will not be registered and the study team will be immediately notified.
- 5. The DCC will send a Confirmation of Registration Form, including the Subject Study Number and cohort assignment to:
 - The study team: Site Lead Investigator, treating physician/ sub-investigator, protocol nurse, CRC and pharmacy (as needed).
 - The COH Study PI and COH study team designees (including but not limited to study monitor(s) and statistician(s)).
- 6. Upon receipt of the Confirmation of Registration Form, COH study team will register the patient in OnCore. The DCC will register non-COH patients in OnCore.

4.3 Screen Failures and Registered Participants Who Do Not begin Study Treatment

Notify the DCC immediately if the participant screen fails after registration or if the participant does not start treatment.

For non-COH sites, the reason for screen failure will be documented in the registration coversheet (Appendix D) and submitted to the DCC.

Issues that would cause treatment delays should be discussed with the Study Principal Investigator.

